**Table 1. Summary of Study procedures\***

Visit	Details
Screening visit	
 
Patient seen in pancreatobiliary clinic for painful chronic pancreatitis
 
Review eligibility criteria
 

Informed consent	
 
Obtain informed consent
 

Run-in period (approximately - 14 to 0 days)	
 
Subject provides daily diary for approximately 14 days (Ecological Momentary Assessment)
 

Quantitative Sensory Testing	
 
Complete Quantitative Sensory Testing prior to randomization procedure
 

Randomization visit (day 0)	
 
Confirm eligibility criteria
 
Finalize completion of baseline assessment instruments
 
Randomization procedures
 

Randomization procedures (day 0)	
 
Complete EUS + sham or EUS + ERCP with pancreatic endotherapy
 
No randomization procedure if observational subject.
 

Telephone contact (day 7)	
 
Telephone contact to confirm no procedure-related adverse events
 

Telephone contact (day 30)	
 
Telephone contact to confirm no procedure-related adverse events
 

Complete Daily Diary (days 0-30 and 76-90)	
 
Subject will complete daily diary for 30 days after randomization procedures (Ecological Momentary Assessment)
 
Subject will complete daily diary for the 14-day period leading up to their follow-up visit (days 76-90), which will be scheduled on day 90
 

Follow-up visit (day 90)	
 
Subject returns for in- person follow-up assessment (repeat baseline assessment instruments and quantitative sensory testing).           
 
Observational subject may complete visit by telephone
 
 
 
Repeat ERCP with pancreatic endotherapy if applicable (if stents are in place and require removal or upsizing)
 
Perform ERCP if failure to improve, subject is unmasked and found to be in sham group, and subject wishes to proceed with pancreatic endotherapy
 
Complete primary outcome measures
 

Follow-up visit (day 180)	
 
Subject completes follow-up assessment (abbreviated version of the baseline assessment)
 
Repeat pancreatic endotherapy scheduled, if applicable
 
Referral for pancreatic surgery, if applicable
 

Follow-up visit (day 270)	
 
Subject completes follow-up assessment (abbreviated version of the baseline assessment)
 
Repeat pancreatic endotherapy scheduled, if applicable
 
Referral for pancreatic surgery, if applicable
 

Follow-up visit (day 360)	
 
Subject completes follow-up assessment (abbreviated version of the baseline assessment)
 
Repeat pancreatic endotherapy scheduled, if applicable
 
Referral for pancreatic surgery, if applicable
 

Study completion visit (day 360)	
 
Complete all study-related activities
 

\* All visits are research-related visits. Please note that endoscopic ultrasound (EUS) and endoscopic retrograde cholangiopancreatography (ERCP) are not experimental procedures since they are used in clinical practice. Given the randomized nature of the study design, the costs for the randomization procedures will be covered by the grant. All follow-up procedures will be billed per usual clinical care.

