### 10.1.3 Follow-up visits, day 0 -90

The subject will be contacted by telephone at day 7 and 30, and complete the Ecological Momentary Assessment during this 30-day period. After the 30 day follow up phone call is complete, the participant will be compensated \$50 for their time. Thereafter, follow-up will

be on an as-needed basis until the subject returns on day 90 for the first formal follow-up assessment (details in *table 3*). The discussion regarding next steps in treatment will occur between the subject, a blinded gastroenterologist, and a blinded hepatobiliary surgeon. A multidisciplinary discussion between patient, endoscopist, and surgeon complies with society guidelines. In the case of medical management, this will be directed by the blinded physicians. In the event of an emergency room or inpatient hospitalization due to abdominal pain or other symptoms potentially attributable to chronic pancreatitis, a blinded physician will determine whether repeat endoscopic or surgical intervention is warranted before the 90-day outcome assessment. In the event that the patient is referred for repeat endoscopic or surgical intervention before reaching the 90-day outcome assessment, the Ecological Momentary Assessment tool will be reactivated in order to capture pain data for up to 14 days leading up to and including the day of intervention, as feasible. Rather than assuming no change from baseline in pain scores for those that have a re intervention prior to day 90, we will capture the pain score prior to re intervention and use these data to calculate the change score for the primary analysis.

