The day 90 follow-up assessment will include completion of selected instruments and a discussion with blinded physician investigators about their clinical course. It is not realistic to assign a threshold pain score above which further intervention should be offered, so it is expected that the blinded physicians and patient will decide whether an intervention is required to treat pain; this highlights the importance of the study's sham design. Potential scenarios are detailed in *figure 2*. Although not incorporated into this study's pilot primary outcome, it is expected that a decision to proceed with an intervention to treat pain would be considered a "failure" of pancreatic endotherapy in a definitive clinical trial. Each of the groups in figure 2 are explained in further detail below. The design of the hierarchical diagram is deliberate and intends to illustrate that management options for groups 3 and 4 are the same. In addition, follow-up is in part dependent on the original treatment allocation. So, after all blinded assessments have been completed and a decision regarding intervention determined, an unblinded investigator will need to advise the subject regarding next steps. Participants will be compensated \$75 after completing the 90-day follow up visit. If participants complete all visits, they will be compensated a total of \$200.

**1. Sham group, no intervention advised.** In this scenario, the subject is doing well enough that no intervention is advised. Since no procedures have been performed until this point, continued medical management is reasonable. The subject would be followed through day 360 for relevant changes in clinical course and to assess secondary endpoints.

[figure not shown]
**2. Endotherapy group, no intervention advised.** In this scenario, the subject is doing well enough that no intervention is advised. Since pancreatic endotherapy had been performed during the randomization procedure, the subject would be advised to undergo repeat pancreatic endotherapy to remove pancreatic duct stents. In some cases, the treating endoscopist may recommend replacing or upsizing stents in an effort to minimize stricture recurrence. This will be determined by the unblinded treating physician per standard of care. Follow-up procedures would be open-label, although it is possible that the subject remain blinded to their original treatment allocation.

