**3. Sham group, intervention advised.** In this scenario, the subject is doing poorly, and an intervention is advised. The blinded physicians will discuss three options with the patient: 1) further medical management, including the initiation or titration of analgesics; 2) pancreatic endotherapy; 3) consideration of surgical interventions.

**4. Endotherapy group, intervention advised.** In this scenario, the subject is doing poorly, and an intervention is advised. The blinded physician investigator will discuss three options

with the patient: 1) further medical management, including the initiation or titration of analgesics; 2) pancreatic endotherapy; 3) consideration of surgical interventions. Since the subject had previously undergone pancreatic endotherapy, the unblinded physician investigator will need to be informed of the recommendation and proceed endoscopy to remove pancreatic duct stents if necessary and applicable.

All procedures performed during the day 90 visit and thereafter will be open-label and are within the spectrum of routine clinical procedures.

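### Table 1, Section 10.1.3 and Section 16.0 disagree on the day-90 rescue path: which arms may have ERCP for failure, and whether the choice comes before or after allocation is disclosed

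*Combined protocol and SAP*

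**What the plan says.** **Table 1, day-90 row.** Two entries allow ERCP. The first is "Repeat ERCP with pancreatic endotherapy if applicable (if stents are in place and require removal or upsizing"). The second is tied to failure: "Perform ERCP if failure to improve, subject is unmasked and found to be in sham group, and subject wishes to proceed with pancreatic endotherapy".

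**Section 10.1.3.** The text declines to set a pain threshold. Instead, "it is expected that the blinded physicians and patient will decide whether an intervention is required to treat pain". Disclosure follows that decision: "after all blinded assessments have been completed and a decision regarding intervention determined, an unblinded investigator will need to advise the subject". On eligible arms, the diagram of scenarios "intends to illustrate that management options for groups 3 and 4 are the same", group 3 being failing sham subjects and group 4 failing endotherapy subjects. For group 3, "The blinded physicians will discuss three options with the patient": medical management, endotherapy or surgery. Group 4 has the same list, and the unblinded physician is told of the recommendation afterwards. The section adds that a decision to intervene for pain is outside the pilot primary outcome but is expected to be a failure criterion in the definitive trial.

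**Section 16.0.** Participants do not learn the results of the initial randomization procedures until the study is complete. Results of any additional procedures may be shared with them.

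**The concern.** Aim 1 is to test whether recruitment, retention and blinding are feasible in a sham-controlled trial. The decision to intervene at day 90 is the candidate failure endpoint for the definitive trial, and Section 10.1.3 presents the blinded way of making it as a reason for having a sham arm. If a subject first learns the allocation and then chooses, a sham subject chooses knowing that nothing was done, and an endotherapy subject chooses knowing that the treatment did not help. A difference between arms in the choice would then mix treatment effect with knowledge of allocation. Disclosure at day 90 can also colour later self-reports, including the patient's global impression of change, which Table 3 collects at days 180, 270 and 360.

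**Working it through.** No calculation applies. The check sets the three places side by side and then follows each type of failing subject through them.

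| Element | Table 1, day 90 | Section 10.1.3 | Section 16.0 |
|---|---|---|---|
| ERCP for failure: which arm | Sham only | Both arms | Not addressed |
| Choice and disclosure | Subject's wish listed after unmasking | Decision by subject and blinded physicians, then unblinded advice | Initial procedure results withheld to study completion |
| Subject told allocation at day 90 | Yes, on this path | Implied by the unblinded advice for some; one scenario says the subject may stay blinded | No |

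1. **Failing sham subject.** Table 1 has the subject unmasked, found to be sham, and wishing to proceed. Section 10.1.3 has blinded physicians discuss the options and a decision reached first. The eligible treatment agrees; the order does not.
2. **Failing endotherapy subject with a stent to be managed.** Table 1 permits ERCP, but because of the stent. Section 10.1.3 permits endotherapy because the subject is doing poorly.
3. **Failing endotherapy subject with no stent to be managed.** Table 1 has no day-90 ERCP entry for this subject. Section 10.1.3 offers endotherapy as one of three options. The gap is confined to day 90: the later rows of Table 1 (days 180, 270 and 360) list repeat endotherapy for either arm where applicable. The subset is probably small, since Section 3.1 says that most such patients need a stent and Section 10.1.2 defines technical success by placing at least one. The documents do not give its size.
4. **Disclosure.** Table 1 makes unmasking a condition of the sham subject's ERCP at day 90. Table 1 also puts study completion at day 360. Section 16.0 therefore holds the procedure results back well past the point at which Table 1 reveals them. Its allowance for additional procedures covers the results of those procedures, not of the initial one.
5. **Where the effect falls.** The primary outcome uses the 14-day diary before the day-90 assessment (days 76 to 90), which precedes rescue at that visit. For re-intervention before day 90, Section 10.1.3 uses pain scores from before the intervention, in both arms alike. The effect on the primary change score is therefore small. What is exposed is the decision to intervene and the follow-up after day 90.

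**The case against.** The strongest reply is that one sequence satisfies both orders: a blinded decision, then unmasking, then confirmation that the subject wishes to proceed. Table 1 is titled a summary, its conditions need not be listed in order of time, and Section 10.1.3 states the order explicitly. The protocol also says that procedures from day 90 on are open-label, and that the decision is not part of the pilot primary outcome. This makes the order conflict modest. It does not remove it: no section states that sequence, and it resolves neither the eligible arms nor Section 16.0.

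Several stronger readings are tempting and are not supported.

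- *A further conflict before day 90.* Section 10.1.3 provides that, after an emergency visit or admission, "a blinded physician will determine whether repeat endoscopic or surgical intervention is warranted before the 90-day outcome assessment". Table 1 is silent on this for both arms, and silence is not a prohibition. This is a difference in coverage.
- *Bias in the primary analysis.* The rule on pre-intervention scores has no arm restriction, and nothing in Table 1 contradicts it.
- *Conflicting triggers.* The absence of a threshold is deliberate and explained. Failure to improve in Table 1 can be read as shorthand for the same clinical judgement.
- *A count of affected subjects.* The sham response rates in Section 2.3 come from sphincter of Oddi dysfunction, with another instrument at 12 months, or from sham procedures in general. They do not measure the difference between Table 1 and Section 10.1.3.

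**Conclusion.** The inconsistency at day 90 is real and rests on the text alone. Table 1 and Section 10.1.3 differ on the eligible arm and, read literally, on whether the choice precedes disclosure; Section 16.0 does not fit the unmasking in Table 1. The consequence is limited to the blinded decision to intervene and to self-reports at days 180 to 360, and it arises only where Table 1 is followed as written. A reader might infer that the two sites will handle failing subjects differently. That is possible while two descriptions stand, but no section says that it will happen, and some variation is intended because the decision is left to judgement. With 15 subjects per arm, a few choices made with knowledge of allocation could blur the comparison of intervention decisions that the pilot is meant to inform. The number cannot be derived from the documents. The point is worth correcting; it does not threaten the primary pain comparison.

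**What to change.** Reconcile the day-90 row of Table 1, Section 10.1.3 and Section 16.0 into one sequence that states who decides, in which arms each option is open, and when allocation is disclosed to the subject. Which clinical rule applies is for the investigators to settle.

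Whichever rule is chosen, have the decision of the subject and blinded physicians (medical management, endotherapy or surgery) entered in WebDCU and locked with a time stamp before allocation is disclosed. Record any later change of choice separately, so that the blinded decision and the treatment actually received can both be reported by arm.

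The cost is a wording amendment and one extra form in the existing database. Non-urgent unmasking would wait until the form is locked; urgent unmasking under Section 14.6 would be unaffected.

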### 10.1.2 Baseline and randomization procedures

The subject will complete baseline instruments detailed in **table 2**. The subject will return on study day 0. Patients will be compensated \$75 for their time completing the baseline assessments. Women of childbearing potential will be administered a urine pregnancy test. If the result is positive for pregnancy, the patient will be excluded from the study. After confirmation of meeting eligibility criteria, the subject will undergo the randomization procedures (endoscopic ultrasound + sham pancreatic endotherapy or endoscopic ultrasound + ERCP with pancreatic endotherapy).

All subjects will undergo anesthesia administered sedation and endoscopic ultrasound (EUS). The endoscopist will assess the pancreas for parenchymal and ductal features of chronic pancreatitis and confirm the absence of exclusion criteria (such as the presence of an occult pancreatobiliary malignancy). Following the completion of the EUS, assuming that eligibility criteria are still met, and while the subject remains under anesthesia, the subject will be randomized to ERCP with pancreatic endotherapy or EUS only (sham). If randomized to sham, the endoscopist will not perform ERCP. To maintain the blind, the patient and clinical team will stay in the endoscopic suite for at least 45 minutes after randomization. This is the average length of time the ERCP with endotherapy could take if randomized to this group.

If randomized to ERCP with pancreatic endotherapy, the endoscopist will proceed with this intervention immediately following the completion of EUS and treatment allocation (during the same anesthesia). Pancreatic endotherapy may include any or all of the following maneuvers: pancreatic endoscopic sphincterotomy, stricture dilation using a bougie or hydrostatic balloon catheter, pancreatic stone extraction with or without mechanical or electrohydraulic lithotripsy, extracorporeal shock wave lithotripsy, and stent placement. Overall technical success will be defined by the ability to insert at least one pancreatic stent across the dominant main pancreatic duct obstruction. Technical success for pancreatic stone treatment will be defined by the ability to remove all fluoroscopically visible main pancreatic duct stones.

At the discretion of the treating physician, patients may be given a medication called an indomethacin suppository to help prevent post-ERCP pancreatitis. Indomethacin is commonly used to prevent post-ERCP pancreatitis in clinical practice based on previous studies, but is not FDA approved for this specific purpose.

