### 1.1. Aim #1. To determine the feasibility of a sham-controlled pancreatic endotherapy trial.

The *PERCePT* study is a pilot, sham-controlled, randomized clinical trial to evaluate the feasibility of recruitment, retention, and blinding procedures, as well as to refine the enrollment criteria for a subsequent definitive clinical trial. Patients with painful chronic pancreatitis and main pancreatic duct obstruction will be randomized to endoscopic ultrasound (EUS) + sham versus EUS + ERCP with pancreatic endotherapy, the latter being defined by the use of extracorporeal or intraductal lithotripsy, stone extraction, stricture dilation, stent placement, or some combination. Pancreatic duct obstruction will be defined by the presence of a main pancreatic duct stone, stricture, or both, with consequential upstream dilation of the main pancreatic duct  $\geq 6\text{mm}$ . After completion of the initial endoscopic intervention, patients will be assessed by individuals blinded to treatment allocation for 90 days. At this time, subjects will complete a comprehensive assessment including measures of pain, quality of life, sleep, mood, functioning, and medication use. All subjects will continue to be followed for 12 months after the randomization procedure to assess longer term outcomes.

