### 14.6 Blinding.

To keep free from bias, the protocol has been carefully developed to minimize risk of unmasking subjects and investigators responsible for evaluating subjects during follow-up. If a subject develops a medical problem where it is important for treating providers to know whether or not an ERCP was performed, there will be a mechanism in place for urgent unmasking of treating provider through the Statistical and Data Coordination Center (SDCC).

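### The 45-minute sham stay is a minimum set at an average ERCP time, not matched to the spread of ERCP times, so time in the suite can carry some information about allocation

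*Combined protocol and SAP*

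**What the plan says.** Under section 10.1.2 every subject has an EUS under anesthesia and is randomized during the same anesthetic. For the control arm the text reads "If randomized to sham, the endoscopist will not perform ERCP". The next sentence is the stay rule: "To maintain the blind, the patient and clinical team will stay in the endoscopic suite for at least 45 minutes after randomization". The reason follows: "This is the average length of time the ERCP with endotherapy could take if randomized to this group". The ERCP arm has its own paragraph, which contains no stay rule and allows wide variation in the work done: "Pancreatic endotherapy may include any or all of the following maneuvers", from sphincterotomy and stenting to several forms of lithotripsy.

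On who must stay blind, section 1.1 says "patients will be assessed by individuals blinded to treatment allocation for 90 days", and section 14.6 says that "the protocol has been carefully developed to minimize risk of unmasking subjects and investigators responsible for evaluating subjects during follow-up". Section 16.0 withholds the results of the randomization procedure from participants until the study is complete. None of these sections mentions procedure or suite times. Section 1.1 also makes masking an object of study: the pilot is to "evaluate the feasibility of recruitment, retention, and blinding procedures".

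**The concern.** A minimum stay equal to the average of the other arm aligns one point of two distributions and leaves their shapes different. If the minimum binds sham only, sham stays cannot fall below 45 minutes, while ERCP stays with that average fall on both sides of it. Anyone who sees the interval then has a clue to the arm.

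This matters because the primary outcome in section 4.1 is self-reported pain. Under section 10.1.3, blinded physicians also judge whether further intervention is needed, including before day 90. Section 2.3 reports that 47% of sham subjects in an earlier sham-controlled ERCP trial had more than a 50% reduction in pain, so expectation may affect this outcome. Tables 1 and 3 list no question asking subjects or assessors to guess the allocation, so a timing leak could pass unnoticed into the definitive trial.

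**Working it through.** **1. The plan's own figure.** The 45 minutes cannot be reproduced. The documents give no duration data, SD, percentile or source for it.

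**2. What follows from the text alone.** If only sham is bound, P(sham stay < 45) = 0. The ERCP average is 45 and the maneuvers vary, so P(ERCP stay < 45) > 0. If both arms are bound, both probabilities are 0 and that clue disappears.

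**3. Illustration of size.** Every input except the 45 minutes and the 15 subjects per arm (section 11.2) is my assumption.
- ERCP stay T is lognormal with mean 45 and CV 0.2, 0.3 or 0.5 (SD 9, 13.5 or 22.5 min). Room time beyond the procedure is ignored.
- Sham stay is 45 plus an exponential overrun with mean m = 0, 5, 10 or 20 min.

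With σ² = ln(1 + CV²), σ = 0.198, 0.294 and 0.472.
- P(T < 45) = Φ(σ/2) = 0.54, 0.56 and 0.59, or about 8 to 9 of 15 ERCP subjects.
- P(T > 60) = 1 − Φ(ln(60/45)/σ + σ/2) = 0.06, 0.13 and 0.20, or about 1 to 3 of 15.
- P(sham > 60) = exp(−15/m) = 0.05, 0.22 and 0.47 for m = 5, 10 and 20, and 0 for m = 0.

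So the meaning of a long stay depends on the overrun. With m = 0 it points to ERCP. With m = 20 it is more common in the sham arm.

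**4. Best accuracy in guessing the arm from suite time alone.** A = 0.5 + TV/2, where TV = ½ Σ |p(sham) − p(ERCP)| over 5-minute bins, from 400,000 simulated stays per arm. Ranges are over the three CVs.

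| Mean sham overrun | Minimum on sham only | Minimum on both arms |
|---|---|---|
| 0 min | 90–96% | 63–66% |
| 5 min | 78–87% | 56–60% |
| 10 min | 77–82% | 65–67% |
| 20 min | 77–80% | 73–76% |

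As a benchmark, drawing sham and ERCP times from one distribution gives 50%.

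**5. If observers see only total time.** Subjects, family and ward staff are more likely to know total time than the randomization time. I added a normal component with an assumed SD of 10 to 20 min in both arms for preparation, EUS and recovery. ERCP SD was 10 to 20 min and mean overrun 0 to 10 min. Accuracy falls to 53–68% (sham only) and 51–60% (both arms). A 20-minute mean overrun raises the upper ends to 70% and 67%.

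**The case against.** The strongest case against has four parts.

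- **Visibility.** The clock starts while the subject is anesthetized, and nothing shows that a blinded person learns the randomization time. At most they see total time, in which EUS and recovery dilute the cue. This stands, and step 5 shows the effect is large. But the plan does not keep the times from anyone either. Section 16.0 covers results and section 14.6 states an aim; neither mentions times.
- **No ceiling.** The rule sets a minimum only, so clustering of sham stays near 45 minutes is an inference. This stands. A reader might infer that any clearly longer stay identifies ERCP. The documents do not support that, and in step 3 the direction reverses when overruns are long.
- **Which arm.** The rule names no arm. If it binds both, no ERCP leaves before 45 minutes and the cue is weaker. Position favours the sham reading, because the rule directly follows the sham sentence and the ERCP paragraph lacks it. The ambiguity still needs resolving.
- **Delay.** The formal blinded assessment is at day 90, long after any day-0 clue. This has some weight, but daily diaries run over days 0–30 and an early belief about allocation could persist.

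**Conclusion.** The point holds in a limited form. As written, the stay is not matched between arms, so suite time can carry some information about allocation, and no section withholds it. In the scenarios tried, best-guess accuracy ran from about 51% to 96%. That width reflects four things the plan does not give: the spread of ERCP times, the sham overrun, the EUS and recovery times, and who sees the times. These figures describe an ideal guesser who knows both distributions; they are not an expected unblinding rate.

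A reader might go further and conclude that suite time defeats the blind, or read the share of ERCP stays above some cut-off as the number of subjects unmasked. The documents support neither. The spread is assumed, the sham clustering is inferred, and an observer without the randomization time cannot apply the cut-off. This is a cheap improvement to a masking procedure that the pilot itself sets out to test, not a flaw that invalidates the trial.

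**What to change.** In section 10.1.2:
1. State that the same 45-minute minimum after randomization applies to both arms, including short or failed ERCPs.
2. Give family and ward staff a common release or notification time regardless of arm.
3. Keep randomization, procedure start and stop, and suite-exit times out of records available to subjects and to the blinded physicians and assessors until the blinded day-90 assessment is complete, subject to the urgent unmasking route in section 14.6.

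The cost is some record handling and room time for short ERCP cases. Under the step 3 assumptions the mean ERCP stay rises from 45 to 48.6–53.4 minutes, since E[max(T, 45)] = 45 + 45(2Φ(σ/2) − 1), which is about 4 to 8 minutes per ERCP case on average. A common minimum removes the clue below 45 minutes but not a difference above it, so items 2 and 3 are needed as well.

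Drawing sham exit times from logged ERCP durations would match the arms more closely, but it is not clearly cheap. It holds some sham subjects longer, and it creates a new cue if only ERCP cases carry the minimum. Sedation and its duration remain a clinical decision and are not part of this change.
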